10.5. Appendix 5: Background Factors

Information on the following will be collected at Visit 1 for all infant participants:

- Educational level of parents
- Exposure to smoke (including tobacco smoke)
- Number of children in the household and if they attend school
- Number of children in household under 5 years of age (under 60 months)
- Number of children in household ≥ 5 years of age (≥ 60 months)

Information on the following will be collected at each postbirth visit, CCI

- Childcare framework (for infant participant)
- Breastfeeding information

10.6. Appendix 6: Abbreviations

The following is a list of abbreviations that may be used in the protocol.

Abbreviation	Term
Abs	absolute
AE	adverse event
Al(OH) ₃	aluminum hydroxide
ALT	alanine aminotransferase
Apgar	appearance, pulse, grimace, activity, and respiration
AST	aspartate aminotransferase
BLQ	below the limit of quantitation
BMI	body mass index
BUN	blood urea nitrogen
CBER	Center for Biologics Evaluation and Research
CFR	Code of Federal Regulations
CI	confidence interval
CIOMS	Council for International Organizations of Medical Sciences
CK	creatinine kinase
CONSORT	Consolidated Standards of Reporting Trials
CRF	case report form
CRO	contract research organization
CSR	clinical study report
CT	clinical trial
DILI	drug-induced liver injury
dLIA	direct-binding Luminex immunoassay
DNA	deoxyribonucleic acid
DU	dispensable unit
EC	ethics committee
eCRF	electronic CRF
EDD	estimated delivery date
e-diary	electronic diary
E-DMC	external data monitoring committee
EDP	exposure during pregnancy
EMA	European Medicines Agency
EU	European Union
EudraCT	European Clinical Trials Database
FIH	first-in-human
FI-RSV	formalin-inactivated respiratory syncytial virus vaccine
GCP	Good Clinical Practice
GGT	gamma-glutamyl transferase
GMFR	geometric mean fold rise
GMR	geometric mean ratio
GMT	geometric mean titer
HBsAg	hepatitis B surface antigen
HBV	hepatitis B virus
HCV	hepatitis C virus
HELLP	hemolysis, elevated liver enzymes, and low platelet count
HIPAA	Health Insurance Portability and Accountability Act
HIV	human immunodeficiency virus
IB	investigator's brochure
ICD	informed consent document

Abbreviation	Term
ICH	International Council for Harmonisation
ID	identification
CCI	[REDACTED]
IND	investigational new drug application
INR	international normalized ratio
IP manual	investigational product manual
IRB	institutional review board
IRC	internal review committee
IRT	interactive response technology
IV	intravenous
IWR	interactive Web-based response
LFT	liver function test
LLOQ	lower limit of quantitation
LMIC	lower- and middle-income country
LMP	last menstrual period
CCI	[REDACTED]
MAE	medically attended adverse event
MCAR	missing completely at random
MedDRA	Medical Dictionary for Regulatory Activities
mITT	modified intent-to-treat
N/A	not applicable
NaCL	sodium chloride
PCD	primary completion date
CCI	[REDACTED]
POC	proof-of-concept
PT	prothrombin time
RBC	red blood cell
RCDC	reverse cumulative distribution curve
RSV	respiratory syncytial virus
RSV A	respiratory syncytial virus subgroup A
RSV B	respiratory syncytial virus subgroup B
CCI	[REDACTED]
SAE	serious adverse event
SAP	statistical analysis plan
SoA	schedule of activities
SOP	standard operating procedure
SRM	study reference manual
SRSD	single reference safety document
SUSAR	suspected unexpected serious adverse reaction
TBili	total bilirubin
Tdap	tetanus, diphtheria, and acellular pertussis vaccine
ULN	upper limit of normal
CCI	[REDACTED]
US	United States
WBC	white blood cell

10.7. Appendix 7: Country-Specific Appendix – Applicable to Argentina Only

The inclusion criterion below replaces Criterion 1 in the original protocol because of the board of health request for the upper age limit for maternal participants to be 39 years:

Section 5.1.1 Inclusion Criteria – Maternal Participants

Age and Sex:

1. Healthy women ≥ 18 and ≤ 39 years of age who are between 24 0/7 and 36 0/7 weeks of gestation on the day of planned vaccination, with an uncomplicated, singleton pregnancy, who are at no known increased risk for complications, and whose fetus has no significant abnormalities observed on ultrasound.

Note: Gestational age must be based upon ultrasound results obtained at ≥ 18 weeks of pregnancy.

1. VERSION HISTORY

Table 1. Summary of Changes

Version/ Date	Associated Protocol Amendment	Rationale	Specific Changes
1/ 13 Aug 2019	Amendment 1/ 18 Jun 2019	N/A	N/A
2 (Amendment 1)/ 18 Nov 2019	Amendment 1/ 18 Jun 2019	
 Updated description of evaluable maternal population as not all maternal subjects will have a 1 month postvaccination visit. Removed a planned analysis and a subset analysis Added details for clarity 	
 Updated the author’s job title Updated the evaluable maternal population (in Section 4) to remove reference to “1 month after vaccination” for the blood draw and to specify time frame of assay results. Updated the evaluable infant population (in Section 4) to make it more time point-specific Updated Section 6.4 (Table 8 and Table 9) to remove the reference to subset analysis for GA subgroup “27 to <33 weeks” Updated Section 7.2 with new information regarding available assay data and added text regarding “preliminary evaluable populations” Updated Section 7.2 to remove reference to a planned analysis on 500 US participants

2. INTRODUCTION

This statistical analysis plan (SAP) provides the detailed methodology for summary and statistical analyses of the data collected in Study C3671003. A brief description of the study design and the study objectives is given below. Subsequent sections describe analysis populations and give the definitions of the safety and immunogenicity endpoints followed by details of statistical reporting. A list of tables, listings and figures, mock-up tables, listings, and figures, and programming rules are prepared separately based on the methods described in this document. This document may modify the plans outlined in the protocol; however, any major modifications of the primary endpoint definition or its analysis will also be reflected in a protocol amendment.

As the first study of Pfizer’s respiratory syncytial virus (RSV) vaccine in the maternal immunization setting, data from this study will be critical for business decisions regarding the future development of the vaccine in maternal immunization. Specifically, this study will determine whether the safety and immunogenicity profile of the vaccine is sufficiently promising for Pfizer to proceed to studies of efficacy. Also, if that is the case, this study will provide the data to select the dose and formulation of the vaccine to be used in future studies. Criteria to be used in making those development decisions are beyond the scope of this SAP.

2.1. Study Objectives, Endpoints, and Estimands

2.1.1. Primary Objectives

2.1.1.1. Primary Objective: Maternal Participants

- To describe the safety and tolerability of an RSV vaccine in women ≥ 18 through 49 years of age who were vaccinated with 1 dose of RSV vaccine during pregnancy.

2.1.1.2. Primary Objective: Infant Participants

- To assess the safety of maternal immunization in infants born to women ≥ 18 through 49 years of age who were vaccinated with 1 dose of RSV vaccine during pregnancy.

2.1.2. Secondary Objectives

2.1.2.1. Secondary Objective: Maternal Participants

- To describe the immune responses elicited by an RSV vaccine in women ≥ 18 through 49 years of age who were vaccinated with 1 dose of RSV vaccine during pregnancy.

2.1.2.2. Secondary Objective: Infant Participants

- To describe RSV antibody levels in infants born to women ≥ 18 through 49 years of age who were vaccinated with 1 dose of RSV vaccine during pregnancy.

CCI

2.1.4. Primary Estimands

2.1.4.1. Primary Estimands: Maternal Participants

- **Percentage of maternal participants reporting local reactions.**

This estimand includes the following 4 attributes:

- Population: Maternal participants who receive 1 dose of investigational product.
- Variable: Presence/absence of prespecified local reactions within 7 days after vaccination.
- Intercurrent event(s): For participants who discontinue, all collected data will be included; missing data will not be imputed.
- Population-level summary: Percentage of maternal participants reporting local reactions in each vaccine group.

- **Percentage of maternal participants reporting systemic events.**

This estimand includes the following 4 attributes:

- Population: Maternal participants who receive 1 dose of investigational product.
- Variable: Presence/absence of prespecified systemic events within 7 days after vaccination.
- Intercurrent event(s): For participants who discontinue, all collected data will be included; missing data will not be imputed.
- Population-level summary: Percentage of maternal participants reporting systemic events in each vaccine group.

- **Percentage of maternal participants reporting adverse events (AEs) from the time of vaccination through 1 month after vaccination.**

This estimand includes the following 4 attributes:

- Population: Maternal participants who receive 1 dose of investigational product.
- Variable: Presence of AEs within 1 month after vaccination.
- Intercurrent event(s): For participants who discontinue, all collected data will be included; missing AE dates will be imputed as described in Pfizer's Vaccine Statistics Rulebook.
- Population-level summary: Percentage of maternal participants reporting AEs through 1 month after vaccination in each vaccine group.

- **The percentage of maternal participants reporting obstetric complications, medically attended adverse events (MAEs), and serious adverse events (SAEs) throughout the study.**

This estimand includes the following 4 attributes:

- Population: Maternal participants who receive 1 dose of investigational product.
- Variable: Presence/absence of the event of interest throughout the study.
- Intercurrent event(s): For participants who discontinue, all collected data will be included; missing AE dates will be imputed as described in Pfizer's Vaccine Statistics Rulebook.
- Population-level summary: Percentage of maternal participants reporting obstetric complications, MAEs, and SAEs throughout the study in each vaccine group.

2.1.4.2. Primary Estimands: Infant Participants

- **Percentage of infant participants with specific birth outcomes.**

This estimand includes the following 4 attributes:

- Population: Infant participants born to the maternal participants receiving 1 dose of investigational product.
- Variable: Presence/absence of specific birth outcomes.
- Intercurrent event(s): No intercurrent events to be taken into account.
- Population-level summary: Percentage of infant participants with specific birth outcomes in each vaccine group.

- **Percentage of infant participants having AEs.**

This estimand includes the following 4 attributes:

- Population: Infant participants born to the maternal participants receiving 1 dose of investigational product.
- Variable: Presence/absence of AEs from birth to 1 month, CCI [REDACTED]
- Intercurrent event(s): For participants who discontinue, all collected data will be included; missing AE dates will be imputed as described in Pfizer's Vaccine Statistics Rulebook.
- Population-level summary: Percentage of infant participants with AEs CCI [REDACTED] from birth to 1 month in each vaccine group.

- **Percentage of infant participants having SAEs, AEs of special interest, and MAEs through 12 months of age.**

This estimand includes the following 4 attributes:

- Population: Infant participants born to the maternal participants receiving 1 dose of investigational product.
- Variable: Presence/absence of SAEs, AEs of special interest, and MAEs. These will be collected through 12 months of age, except for those congenital anomalies that occur during intrauterine life and can be identified prenatally, at birth, or later in life.
- Intercurrent event(s): For participants who discontinue, all collected data will be included; missing AE dates will be imputed as described in Pfizer's Vaccine Statistics Rulebook.
- Population-level summary: Percentage of infant participants with the event of interest during the first 12 months of life in each vaccine group.

2.1.5. Secondary Estimands

2.1.5.1. Secondary Estimands: Maternal Participants

- **Immune response estimated by the geometric mean titer (GMT) for RSV A– and RSV B–neutralizing antibody titers.**

This estimand estimates the vaccine effect in the hypothetical setting where participants follow the study schedules and protocol requirements as directed. It includes the following 4 attributes:

- Population: Maternal participants receiving 1 dose of investigational product and in compliance with key protocol criteria (evaluable participants).
- Variable: Antibody titer results before vaccination, 2 weeks and 1 month after vaccination, and at delivery.
- Intercurrent event(s): For participants who discontinue or have major protocol violations, all postdiscontinuation or postviolation observations will be censored. Results obtained from out-of-window blood draws will also be removed. Missing serology results will not be imputed, as missing completely at random (MCAR) is assumed.
- Population-level summary: GMT for RSV A– and RSV B–neutralizing antibody titers.

- **Immune response estimated by the geometric mean fold rise (GMFR) from baseline in RSV A– and RSV B–neutralizing antibody titers.**

This estimand estimates the vaccine effect in the hypothetical setting where participants follow the study schedules and protocol requirements as directed. It includes the following 4 attributes:

- Population: Maternal participants receiving 1 dose of investigational product and in compliance with key protocol criteria (evaluatable participants).
 - Variable: Fold rise from before vaccination to 2 weeks and 1 month after vaccination and at delivery in antibody titers.
 - Intercurrent event(s): For participants who discontinue or have major protocol violations, all postdiscontinuation or postviolation observations will be censored. Results obtained from out-of-window blood draws will also be removed. Missing serology results will not be imputed, as MCAR is assumed.
 - Population-level summary: GMFR from baseline for RSV A– and RSV B–neutralizing antibody titers.
- **Geometric mean ratio (GMR) estimated by the ratio of the GMT for RSV A– and RSV B–neutralizing antibody titers of the RSV vaccine group to the placebo group.**

This estimand estimates the vaccine effect in the hypothetical setting where participants follow the study schedules and protocol requirements as directed. It includes the following 4 attributes:

- Population: Maternal participants receiving 1 dose of investigational product and in compliance with key protocol criteria (evaluatable participants).
- Variable: Antibody titers before vaccination, 2 weeks and 1 month after vaccination, and at delivery.
- Intercurrent event(s): For participants who discontinue or have major protocol violations, all postdiscontinuation or postviolation observations will be censored. Results obtained from out-of-window blood draws will also be removed. Missing serology results will not be imputed, as MCAR is assumed.
- Population-level summary: GMR estimated by the ratio of the GMT for RSV A– and RSV B–neutralizing antibody titers of the RSV vaccine group to the placebo group.

2.1.5.2. Secondary Estimands: Infant Participants

- **Functional antibody levels estimated by the GMT for RSV A– and RSV B–neutralizing antibody titers.**

This estimand estimates the vaccine effect in the hypothetical setting where participants follow the study schedules and protocol requirements as directed. It includes the following 4 attributes:

- Population: Infants born to maternal participants receiving 1 dose of investigational product and in compliance with key protocol criteria (evaluable participants).
- Variable: Antibody titers at birth and at 1, 2, 4, and 6 months of age.
- Intercurrent event(s): For participants who discontinue or have major protocol violations, all postdiscontinuation or postviolation observations will be censored. Results obtained from out-of-window blood draws will also be removed. Missing serology results will not be imputed, as MCAR is assumed.
- Population-level summary: GMT for RSV A– and RSV B–neutralizing antibody titers.

- **GMR estimated by the ratio of the GMT for RSV A– and RSV B–neutralizing antibody titers of the RSV vaccine group to the placebo group.**

This estimand estimates the vaccine effect in the hypothetical setting where participants follow the study schedules and protocol requirements as directed. It includes the following 4 attributes:

- Population: Infants born to maternal participants receiving 1 dose of investigational product and in compliance with key protocol criteria (evaluable participants).
- Variable: Antibody titers at birth and at 1, 2, 4, and 6 months of age.
- Intercurrent event(s): For participants who discontinue or have major protocol violations, all postdiscontinuation or postviolation observations will be censored. Results obtained from out-of-window blood draws will also be removed. Missing serology results will not be imputed, as MCAR is assumed.
- Population-level summary: GMR estimated by the ratio of the GMT for RSV A– and RSV B–neutralizing antibody titers of the RSV vaccine group to the placebo group.

CCI

CCI

CCI

2.2. Study Design

This is a Phase 2b, multicenter, randomized, placebo-controlled, observer-blinded study in which approximately 650 healthy pregnant women ≥ 18 through ≤ 49 years of age will be randomized to receive one of 2 dose levels of bivalent (RSV subgroup A and subgroup B) RSV vaccine candidate at 120 μg (60 μg A and 60 μg B) and 240 μg (120 μg A and 120 μg B) of the prefusion RSV F antigen, formulated with or without aluminum hydroxide ($\text{Al}[\text{OH}]_3$), or placebo (1:1:1:1 randomization). Assessments will include descriptions of safety, tolerability, and immunogenicity in maternal participants as well as safety and characteristics of transplacentally transferred antibodies in their infants. CCI [REDACTED]

[REDACTED] vaccination of mothers will occur at a time of year such that the infant is likely to be exposed to RSV during the first 6 months of life.

This study will use stopping rules. An internal review committee (IRC) and an external data monitoring committee (E-DMC) will monitor safety in this study.

3. ENDPOINTS AND BASELINE VARIABLES: DEFINITIONS AND CONVENTIONS

3.1. Primary Endpoints

3.1.1. Primary Endpoints: Maternal Participants

- Prespecified local reactions within 7 days after vaccination.
- Prespecified systemic events within 7 days after vaccination.
- AEs from the time of vaccination through 1 month after vaccination.
- Obstetric complications, MAEs, and SAEs throughout the study.

3.1.2. Primary Endpoints: Infant Participants

- Specific birth outcomes.
- AEs from birth to 1 month of age CCI [REDACTED].
- SAEs, AEs of special interest (major congenital anomalies, developmental delay), and MAEs through 12 months of age. Major congenital anomalies (defined as structural or functional anomalies [eg, metabolic disorders] that occur during intrauterine life and can be identified prenatally, at birth, or later in life).

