3.2. Infant Participant

Primary Objective Infant Participant	Estimands	Primary Endpoints Infant Participant
To assess the safety of maternal immunization in infants born to women ≥ 18 through 49 years of age who were vaccinated with 1 dose of RSV vaccine during pregnancy	In infant participants born to the maternal participants receiving 1 dose of investigational product: 
• The percentage of infant participants with specific birth outcomes• The percentage of infant participants having AEs• The percentage of infant participants having SAEs, AEs of special interest (congenital anomalies, developmental delay), and MAEs	
• Specific birth outcomes• AEs from birth to 1 month of age• SAEs, AEs of special interest (congenital anomalies, developmental delay), and MAEs through 12 months of age• Congenital anomalies (defined as structural or functional anomalies [eg, metabolic disorders] that occur during intrauterine life and can be identified prenatally, at birth or later in life²⁶)

Secondary Objective Infant Participant	Estimands	Secondary Endpoints Infant Participant

To describe RSV antibody levels in infants born to women ≥ 18 through ≤ 49 years of age who were vaccinated with 1 dose of RSV vaccine during pregnancy
	
In infant participants born to maternal participants receiving 1 dose of investigational product and in compliance with the key protocol criteria (evaluable participants):
 
 • Functional antibody levels estimated by the GMT for RSV A– and RSV–B neutralizing antibody titers • GMR, estimated by the ratio of the GMTs for RSV A– and RSV–B neutralizing antibody titers of the RSV vaccine group and the placebo group 	
 • RSV A– and RSV B–neutralizing antibody titers measured at: 
 • birth • 1 month • 2 months • 4 months • 6 months 
Note: Infant participants will be randomly assigned to 1 of 2 blood sampling schedules.

CCI

CCI

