9.4.2.1. Analysis of the Primary Safety Endpoints

The safety endpoints are primary in the study and their analyses are based on the safety populations. Safety data will be analyzed separately for maternal participants and infants participants. Maternal participants will be analyzed according to the investigational product received, and infant participants will be analyzed according to the investigational product their mothers (maternal participants) received.

The safety analyses for maternal participants are descriptive evaluations of local reactions, systemic events, AEs, obstetric complications, MAEs, and SAEs. Obstetric complication will be defined and identified by the Pfizer study clinician prior to study unblinding. The safety analyses for infant participants are descriptive evaluations of birth outcomes, AEs, SAEs, AEs of special interest (congenital anomalies, developmental delay), and MAEs. AEs and SAEs will be categorized according to MedDRA terms. The number and percentage of participants reporting each event and 2-sided 95% exact CIs will be provided by vaccine group.

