3.5. Safety Endpoints

3.5.1. Adverse Events

AEs will be captured and reported in accordance with Pfizer reporting standards.

For maternal participants the time period for actively eliciting and collecting AEs and SAEs (“active collection period”) begins from the time the maternal participant provides informed consent, which is obtained before participation in the study (ie, before undergoing any study-related procedure and/or receiving investigational product), through and including a minimum of 1 month (30 days) after the last administration of the investigational product. In this study, the investigator and site staff will ensure the active elicitation and collection of AEs and SAEs through 1 month after vaccination. From 1 month after vaccination until the maternal participant completes the study, MAEs and SAEs will be collected.

For infant participants, the time period for actively eliciting and collecting AEs and SAEs (“active collection period”) begins at birth and continues through and including a minimum

of 28 days after birth. From Visit 2 until the last study visit, only AEs of special interest, MAEs, and SAEs, including hospitalizations, will be reported.

For maternal participants who are screen failures, the active collection period ends when screen failure status is determined. If the participant withdraws from the study and also withdraws consent for the collection of future information, the active collection period ends when consent is withdrawn.

During the active collection period, both nonserious AEs and SAEs are recorded on the case report form (CRF) and will be categorized according to the current version (at the time of reporting) of the Medical Dictionary for Regulatory Activities (MedDRA).

An immediate AE is defined as any AE that occurred within the first 30 minutes after administration of the investigational product for maternal participants.

An MAE is defined as a nonserious AE that results in an evaluation at a medical facility. From Visit 2 (for infant participants) or from 1 month after vaccination (for maternal participants) until the participant completes the study, MAEs and SAEs will be collected.

AEs of special interest for infant participants are major congenital anomalies and developmental delays and are collected from birth through the end of the study (12-month-of-age visit).

CCI

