6.1.2.2. AEs Within 1 Month of Age

- Analysis set: Safety (Section 4).
- Analysis methodology: Descriptive summary statistics for Tier 3 events; difference and 95% CI between the vaccine group and the placebo group for Tier 2 events.
- Intercurrent events and missing data: For participants who discontinue, all collected data will be included; missing AE dates will be imputed as described in Pfizer's Vaccine Statistics Rulebook.
- For each group, number of participants with AEs **CCI** within 1 month (30 days) (n), %, and 95% CI will be presented for any AE, each SOC, and each PT within each SOC, by vaccine group. For AEs classified as Tier 2 events, difference in proportions and associated 2-sided 95% CI between the vaccine group and the placebo group will be presented.

6.1.2.3. AEs of Special Interest (Major Congenital Anomalies, Developmental Delays), MAEs, and SAEs Through 12 Months of Age

- Analysis set: Safety (Section 4).
- Analysis methodology: Descriptive summary statistics.
- Intercurrent events and missing data: For participants who discontinue, all collected data will be included; missing AE dates will be imputed as described in Pfizer's Vaccine Statistics Rulebook.
- For each group, number of participants with AEs of special interest, MAEs, and SAEs through 12 months of age (n), %, and 95% CI will be presented for any event, each SOC, and each PT within each SOC, by vaccine group. For AEs of special interest, difference in proportions and associated 2-sided 95% CI between the vaccine group and the placebo group will be presented.

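### Does the SAP's word 'major' change which congenital anomalies count as infant adverse events of special interest?

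*SAP*

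**What the plan says.** SAP Section 3.1.2 gives the infant primary endpoint as "SAEs, AEs of special interest (major congenital anomalies, developmental delay), and MAEs through 12 months of age" and then explains the first term: "Major congenital anomalies (defined as structural or functional anomalies [eg, metabolic disorders] that occur during intrauterine life". Protocol Section 3.2 carries the same explanation under the shorter term: "Congenital anomalies (defined as structural or functional anomalies [eg, metabolic disorders] that occur during intrauterine life". Protocol Section 9.4.2.1, on the analysis, likewise has "AEs of special interest (congenital anomalies, developmental delay), and MAEs".

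On timing, SAP Section 3.5.1 says that the infant events of special interest "are major congenital anomalies and developmental delays and are collected from birth through the end of the study", which it places at the 12-month visit. The estimand in SAP Section 2.1.4.2 sets a 12-month limit on collection and then qualifies it: "except for those congenital anomalies that occur during intrauterine life and can be identified prenatally, at birth, or later in life". The population-level summary of that same estimand is "Percentage of infant participants with the event of interest during the first 12 months of life in each vaccine group".

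The output that depends on the definition is in SAP Section 6.1.2.3: "For AEs of special interest, difference in proportions and associated 2-sided 95% CI between the vaccine group and the placebo group will be presented".

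**The concern.** Two things look wrong. First, label and definition disagree. 'Major' appears in SAP Sections 3.1.2 and 3.5.1 and in the heading of 6.1.2.3, but the visible text gives no severity criterion, code list or classification step. A reader could keep every anomaly, by the definition, or drop minor ones by a rule that is not written down.

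Second, the windows do not match. The estimand variable appears to free congenital anomalies from the 12-month limit, its own summary restores the limit, and Section 3.5.1 starts at birth although the definition includes anomalies identified prenatally.

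The stake would be a component of a primary infant endpoint in the first study of this vaccine in pregnant women and their infants. Within Section 6.1.2.3, events of special interest are the only class given a difference from placebo, so their content matters for that output.

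**Working it through.** The plan states no figure on this point, so the check is mainly a comparison of texts.

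**Step 1: which anomalies count.**

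| Place | Term used | Criterion attached |
|---|---|---|
| Protocol 3.2 | congenital anomalies | structural or functional, arising in utero, found at any time |
| Protocol 9.4.2.1 | congenital anomalies | none added |
| SAP 2.1.4.2 | congenital anomalies | the same in-utero and any-time phrase |
| SAP 3.1.2 | major congenital anomalies | the same definition as Protocol 3.2 |
| SAP 3.5.1 | major congenital anomalies | none added in the visible text |
| SAP 6.1.2.3, heading | major congenital anomalies | none added |

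The only definition anywhere is the protocol's. A defined term takes its definition, so the SAP's set equals the protocol's set and the change in any count is 0. The other reading has to set aside the definition in Section 3.1.2 and the wording of the estimand, and then supply a rule that the visible text does not contain. Both documents also say that a major modification of a primary endpoint definition would appear in a protocol amendment (Protocol Section 9, SAP Section 2). Both SAP versions are tied to Amendment 1, whose current text says congenital anomalies. That fits the reading that no restriction was meant.

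**Step 2: the window.** Infants take part from birth to about 12 months (Protocol 4.1.1). The last infant visit falls at 350 to 378 days (Protocol 1.3.2 and 8.10.2.6), and the study ends at the last visit (Protocol 4.4). No scheduled collection follows, so the exception in the estimand variable has almost nothing to add. If 12 months is taken as 365 days (an assumption), the wordings can differ only over 378 − 365 = 13 days at the end of the last visit window.

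At the other end, any congenital abnormality is recorded at Visit 1 (Protocol 8.10.2.1), whenever it was first seen. Fetal events are collected under the mother from consent (Protocol 8.3.1). Starting infant collection at birth therefore does not lose anomalies seen prenatally. The exception itself follows the protocol, where congenital anomalies form a separate endpoint bullet with no time limit (Protocol 3.2).

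**Step 3: what would be lost if 'major' were applied as a restriction.**

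- Major anomalies, whenever found: difference from placebo under either reading.
- Minor anomalies recorded at birth: difference from placebo under either reading, because malformation or anomaly (yes/no) is a birth outcome (SAP 3.5.7) and birth outcomes get a difference with a 95% CI (SAP 6.1.2.1).
- Minor anomalies first found after birth: still serious adverse events by definition (Protocol 10.3.2), tabulated by group with n, % and 95% CI by system organ class and preferred term through 12 months (SAP 6.1.2.3). Only the printed difference could go.

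**Step 4: scale.** The documents give no anomaly rate and no share that is major, so the number in the last category cannot be derived. For orientation only, take at most 650/5 = 130 infants per group and an assumed equal rate p. The rough half-width of a 95% CI for the difference is 1.96 × √(2p(1 − p)/130). This gives 2.4 points at p = 1%, 4.1 at 3% and 5.3 at 5%. These rates are assumptions, and the SAP's own interval is the Chan and Zhang one. The intervals are wide relative to the rates under either reading.

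**The case for a change.** The strongest reply is that the SAP uses the word three times and never says that it has no effect. A programmer may take it as a restriction, and the serious-event tables carry no difference from placebo. The tier rule is only a partial backstop. In SAP Section 3.5.1 a preferred term needs 4 or more participants in a group within 30 days, so an anomaly first found later would get no difference unless it counted as an event of special interest. The sponsor's team is blinded only until the first planned analysis (Protocol 6.3.2), so the question could be settled with results in view. The wording would also be cheap to correct.

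Part of this stands. The mismatch is real, and so is the disagreement between the estimand's variable and its summary. The rest carries less weight. The tier threshold describes when a difference is printed and does not measure the effect of 'major'; the protocol's own tier rule (Section 9.4.2) has no 30-day limit. The counts by group are reported in any case, so a reader can form the difference for a given term. The claim that no criterion exists cannot be made firmly either: text next to the relevant sentence in SAP Section 3.5.1 is redacted, and SAP Section 2 says that table shells and programming rules are prepared separately. A low cost of rewording does not show a gain when the text followed as written already gives the protocol's set.

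**Conclusion.** The concern identifies a clerical inconsistency and not a fault in the analysis. Read by its definition, the SAP's event of special interest is the protocol's, and the change in results is 0. The window wordings differ over at most about 13 days at the final visit. Under the less natural reading, the most that could be lost is one descriptive difference and its interval, for minor anomalies first found after birth. Those events would still be counted and shown by group.

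The conclusion rests on three assumptions: that analysts apply the definition given in SAP Section 3.1.2, that congenital anomalies are recorded as serious events as Protocol Section 10.3.2 provides, and that 12 months means about 365 days. Because SAP Section 5.1 sets no hypothesis test and no decision rule, no error rate, power figure or planned decision depends on the point. Tidying the term would be harmless, but it is not a change that the plan needs.
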